11.2 Recording/ Documentation of AEs

At each contact with the participant, information regarding adverse events will be elicited by appropriate questioning and examinations, and will be recorded immediately on a source

Protocol IN-CA-311-3963/CTN 299: Version 5.0 Date: March 19, 2019

Page 30 of 53

document (e.g., progress notes, laboratory reports, survey tools, and data collection tools). The start date, stop date, severity of each reportable event, and the PI's judgment of the AE's relationship to the study medication/intervention will also be recorded in the case report form (CRF).

11.3 Serious Adverse Events (SAEs)

A Serious Adverse Event is defined as an AE meeting one of the following:

- Death during the period of protocol-defined surveillance
- Life Threatening Event (immediate risk of death at the time of the event)
- In-patient hospitalization or prolongation of existing hospitalization during the period of protocol-defined surveillance
- Results in congenital anomaly or birth defect
- Results in a persistent or significant disability/incapacity
- Any other important medical event that may not result in one of the above outcomes may be considered a serious adverse event when: based upon appropriate medical judgment, the event may jeopardize the participant, and may require medical or surgical intervention to prevent one of the outcomes listed above. Examples of such medical events include allergic bronchospasm requiring intensive treatment in an emergency room or at home, blood dyscrasias, or convulsions that do not result in in-patient hospitalization, or the development of drug dependency or drug abuse or any event of possible drug-induced liver injury with hyperbilirubinemia defined as ALT>3xULN and bilirubin >2xULN (>35% direct)

Any AE that occurs between baseline and 30 days following the last study visit at Week 96 (or at the time of early discontinuation of the participant from the study for any reason) is to be recorded in the source documentation (patient will be called). Surveillance for AEs will end at 30 days following Week 96. If an SAE is ongoing at the time a participant discontinues/completes the trial the SAE will be followed until the Investigator agrees that the event is satisfactorily resolved, becomes chronic, or that no further follow-up is required.

11.4 AE/SAE Grading, Relationship Assignment and Reporting Procedures

11.4.1 AE/SAE Grading

The intensity (severity) of each adverse/serious event will be graded according to the toxicity table and toxicity guidelines provided by the Division of AIDS (DAIDS) Table for Grading the Severity of Adult and Pediatric Adverse Events. The DAIDS Table will be provided with the Operations Manual.

11.4.2 Relationship Assessment

For all collected AEs (including SAEs), the clinician who examines and evaluates the participant will determine the AE's causality based on temporal relationship and his/her clinical judgment. The degree of certainty about causality will be graded using the categories below:

Definitely Related: There is clear evidence to suggest a causal relationship, and other possible contributing factors can be ruled out. The clinical event, including an abnormal laboratory test result, occurs in a plausible time relationship to drug administration and cannot be explained by concurrent disease or other drugs or chemicals. The response to withdrawal of the drug (de-challenge) should be clinically plausible. The event must be pharmacologically or phenomenologically definitive, with use of a satisfactory re-challenge procedure if necessary.

Probably Related: There is evidence to suggest a causal relationship, and the influence of other factors is unlikely. The clinical event, including an abnormal laboratory test result, occurs within a reasonable time sequence to administration of the drug, is unlikely to be attributed to concurrent disease or other drugs or chemicals, and follows a clinically reasonable response on withdrawal (de-challenge). Re-challenge information is not required to fulfill this definition.

Possibly Related: There is some evidence to suggest a causal relationship (e.g., the event occurred within a reasonable time after administration of the trial medication). However, the influence of other factors may have contributed to the event (e.g., the participant's clinical condition, other concomitant events). Although an adverse drug event may rate only as "possibly related" soon after discovery, it can be flagged as requiring more information and later be upgraded to "probably related" or "definitely related", as appropriate.

Unlikely: A clinical event, including an abnormal laboratory test result, whose temporal relationship to drug administration makes a causal relationship improbable (e.g., the event did not occur within a reasonable time after administration of the trial medication) and in which other drugs or chemicals or underlying disease provides plausible explanations (e.g., the participant's clinical condition, other concomitant treatments).

Not related: The AE is completely independent of study drug administration, and/or evidence exists that the event is definitely related to another etiology. There must be an alternative, definitive etiology documented by the clinician.

11.4.3 SAE Reporting Procedures

The Investigator or designee must report any SAE occurring in a patient receiving study drug to the Sponsor within 24 hours, even if the SAE is not drug-related. This should be done by telephone and by sending a faxed or emailed copy of the Serious Adverse Event form plus other supporting documentation, as required.

SAEs will be reported to:

Immunodeficiency Clinic

University Health Network

Attention: [name], Research Nurse Manager

[contact] [name] or [contact]

[contact]

E-mail: [contact]

All additional follow-up evaluations must also be reported as soon as possible in the same manner. All SAEs will be followed until the Investigator agrees that the event is satisfactorily resolved, becomes chronic, or that no further follow-up is required.

The Sponsor or designee will be responsible for notifying the relevant authorities of any reportable SAE as outlined in the Canadian Food and Drug Regulations and ICH Guidelines.

The Sponsor will also ensure that other participating Investigators are notified of any SAEs. The Investigator is responsible for ensuring that their local Research Ethics Board (REB) is notified of any SAEs.

11.5 AEs/SAEs monitoring

Any AE/SAE that occurs between baseline and the time the participant departs the study at the end of the final follow-up visit (or at the time of early discontinuation of the participant from the study for any reason) will be captured and recorded in the source documentation. At each contact with the participant, the investigator (or designate) must seek information on adverse events by specific questioning and, as appropriate, by examination.

Adverse events that had previously been reported by the study participant will also be reassessed for duration, intensity and possible reoccurrence. Assessment of safety will include clinical observation and monitoring of routine hematology and biochemistry.

Surveillance for AEs will end 30 days post Week 96 (or at the time of early discontinuation of the participant from the study for any reason). If an SAE is ongoing at the time a participant discontinues/completes the study, the SAE will be followed up until the Investigator agrees that the event is satisfactorily resolved, becomes chronic, or that no further follow-up is required.

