8.4 Final Study Visit (Week 96 +/- 14 days)

The duration of the study is 2 years per participant. Participants will be recruited during the first year of the study and will be followed for 96 weeks. The final visit will be the participant's last follow-up visit and the following assessments will take place:

- Complete Physical Exam
- Vital Signs
- Hematology and biochemistry: CBC with differential and liver profile (AST, ALT), serum creatinine, calcium, phosphate, Urinalysis, GFR, Urine albumin/creatinine, urine protein/creatinine, lipids- cholesterol, LDL, HDL, TG, glucose. CD4/CD8
- Urine pregnancy test and FSH (if premenopausal)
- HIV Viral Load
- Research Blood Sample
- Questionnaires- quality of life, adherence, falls, balance
- Frax Score determined by country specific FRAX calculator
- Framingham Cardiovascular Risk Score
- Medication review: ART and Other Concomitant Medications
- Imaging as per study site: DXA, TBS, HRpQCT
- Geriatric assessment, with questionnaires (frailty, quality of life, balance, falls), dynamometer, performance walking test.

To collect any information on potential adverse event reaction, patients will be called 4 weeks after their last visit at 96 weeks +/- 7 days.

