11. ASSESSMENT OF SAFETY

11.1 Adverse Events (AEs)

Adverse events (AEs) are defined as any untoward medical occurrence in a participant that does not necessarily have a causal relationship with the study medication/intervention. An AE can therefore be any unfavourable and unintended sign (including abnormal laboratory finding), symptom, or disease temporally associated with the use of study drug/intervention, whether or not it is related to the medication/intervention.

Toxicities will be graded on a 4-point scale according to standard guidelines outlined in the “Division of AIDS Table for Grading the Severity of Adult and Pediatric Adverse Events”⁴⁸[Appendix C]. In general, grade 1 and 2 events will not be considered adverse events, but details should be documented in the source documents. Fractures will be considered and captured as an adverse event regardless of grading.

Stable chronic conditions which are present prior to clinical study entry and do not worsen are not considered adverse events and will be accounted for in the participant's medical history.

Participants who have an adverse event should be followed and treated by the site Investigator until the abnormal parameter or symptom has resolved or stabilized. It is up to the clinician to determine that the AE is either resolved or that it has reached a stable state, after which no further follow-up is necessary. There should also be source documentation to support this determination.

Rates of adverse events, serious adverse events and hospitalisations will be compared between the two arms. Specific attention will be paid to HIV RNA (see below), CD4 cell counts, and metabolic parameters such as fasting glucose, and lipid profiles.

The most common adverse reactions of moderate to severe intensity and incidence $\geq 2\%$ in those receiving TAF are headache, fatigue, nasal congestion and diarrhea.

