11.6 Toxicities/ Adverse Event Management

In the event of a discontinuation of TAF/FTC for suspected renal impairment, or other clinically significant chemistry elevations, participants should not restart TDF/FTC or TAF/FTC due to the risk of a recurrent reaction; such participants should be withdrawn from study and seek/be reviewed for alternative antiretroviral therapy. If they agree, participants will continue to be followed for the duration of the study.

11.7 Management of HIV Virologic failure.

Virologic failure must be considered for any patient with plasma HIV RNA ≥ 50 c/mL at any time following randomization. For the purposes of clinical management in this study, virologic failure is defined as:

Two consecutive plasma HIV RNA ≥ 50 c/mL within four weeks of the initial suspected virologic failure.

Cases of confirmed virologic failure will trigger genotypic virologic resistance testing, including integrase resistance testing, when plasma HIV RNA >400 c/mL. The virologic failure definition is intended for guidance and Investigators should use their discretion as to the most appropriate clinical management of their patients. The choice of antiretroviral therapy will be left to the discretion of the treating physician. In some cases, e.g. if there is no evidence of acquired resistance to the current regimen, treatment may be continued with increased efforts at adherence support.

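### Read literally, section 11.5 stops adverse-event surveillance the day a woman leaves the study early, so new events after departure are not sought; 11.3, 11.5 and 11.6 also disagree on the end point

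*Combined protocol and SAP*

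**What the plan says.** Section 11.5 sets the end of surveillance: "Surveillance for AEs will end 30 days post Week 96 (or at the time of early discontinuation of the participant from the study for any" […], whatever the reason for leaving. The first sentence of the same section has a different limit. It captures events up to "the time the participant departs the study at the end of the final follow-up visit", or up to early discontinuation, and gives no extra 30 days to anyone.

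Section 11.3 describes what is recorded: "Any AE that occurs between baseline and 30 days following the last study visit at Week 96 (or at the time of early discontinuation" from the study. It notes in brackets that the patient is telephoned, and then ends surveillance 30 days after week 96 with no exception for early leavers.

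The telephone call is set up in section 8.4: "patients will be called 4 weeks after their last visit at 96 weeks +/- 7 days". The schedule in section 8.7 shows it as the W100 column. Section 8.5, on early termination, asks for the reason and for the final-visit investigations. It does not mention a call.

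Section 11.6 concerns women who stop TAF/FTC for a suspected renal problem or other marked chemistry abnormality: "such participants should be withdrawn from study and seek/be reviewed for alternative antiretroviral therapy". Its next sentence lets them be followed to the end of the study if they agree. Section 8.3 makes the same offer to anyone who decides to stop study medication. Section 11.1 states the use of the data: "Rates of adverse events, serious adverse events and hospitalisations will be compared between the two arms".

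**The concern.** The length of time over which new events are looked for depends on how a woman leaves the trial. A completer is asked about events after her last visit. A woman who leaves early is examined on departure and then, on the literal text of 11.5, not asked again. Some early departures are for clinical reasons: section 10 ends participation when staff or the treating provider judge that continuing would be detrimental, and when virologic failure requires another regimen. New events in the weeks after such a departure are relevant to safety, and no procedure is assigned to find them.

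The conflicting wording adds to this. Sites can apply different windows to the same situation and each can point to a sentence that supports it.

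**Working it through.** There is no stated figure to reproduce. The check is a comparison of the text, followed by arithmetic for scale.

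**Step 1. Where each place ends surveillance**

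- 11.5, first sentence: completer, the final visit; early leaver, the time of discontinuation.
- 11.5, later sentence: completer, 30 days after week 96; early leaver, the time of discontinuation (0 days after).
- 11.3, recording sentence: completer, 30 days after week 96; early leaver, unclear. The bracket can mean 30 days after discontinuation or the moment of discontinuation.
- 11.3, next sentence: 30 days after week 96, with no separate rule for early leavers.
- 8.4 and the W100 column: one call, dated from the week 96 visit.
- 8.5: final-visit investigations, no call.

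Section 11.5 contradicts itself for completers. Sections 11.3 and 11.5 cannot be shown to agree for early leavers. Section 11.6 describes the same women as withdrawn from the study and as followed for its duration.

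**Step 2. What other text covers an early leaver**

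- An existing adverse event is followed until it resolves or stabilises (11.1).
- A serious event still open at discontinuation is followed until resolved, chronic, or no longer needing follow-up (11.3, 11.5).
- A woman who stops drug but agrees to remain is followed (8.3, 11.6). The cut-off in 11.5 is leaving the study, not stopping the drug.

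None of these reaches an event that begins after a woman has left the study. The uncovered group is therefore new-onset events in women who leave and do not stay in follow-up. Section 10 itself makes no offer of continued follow-up.

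**Step 3. Scale**

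Inputs: 128 women (13.1); 10% dropout before week 48 (13.7); less than 1% stopping medication for adverse events in earlier switching studies (1.4).

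- Leavers before week 48: 128 × 0.10 = 12.8, about 13. This is an upper figure for that period, since it counts dropout for any reason and some of these women cannot be contacted. Women leaving between weeks 48 and 96 are additional; the protocol gives no rate for them.
- Days not covered if all could be reached: 12.8 × 30 = 384 woman-days.
- Planned surveillance if all complete: 96 × 7 + 30 = 702 days each; 128 × 702 = 89,856 woman-days. Share: 384 / 89,856 = 0.4%.
- Women stopping for an adverse event, assuming the earlier studies' rate applies here: below 128 × 0.01 = 1.28, so about one.

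**Step 4. The completers' call**

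Four weeks ± 7 days is day 21 to day 35. A call on day 21 leaves 30 − 21 = 9 days of the stated window unasked, so the completers' 30 days are not fully secured either.

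**The case against.** The strongest reply is that this is a drafting inconsistency and not a deliberate two-tier rule. The bracket in 11.3, with its reference to a call, can be read as giving early leavers 30 days. A site might also take 8.5 to import everything in 8.4, call included. Known events and open serious events are followed in any case, and women who stop drug are offered continued follow-up. Those who decline may also decline a call.

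Much of this stands, and it rules out a stronger reading: that women who leave because of toxicity have no cover after treatment. The documents do not support that. The withdrawal wording in 11.6 is followed at once by the offer of follow-up for the duration of the study. Nor do they show that the completers' 30 days are off-drug time: the schedule marks drug dispensation at week 96, and nothing says that TAF/FTC stops there. Leaving the study likewise need not mean stopping antiretrovirals.

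The reply does not close the gap. Section 8.5 names investigations only, 8.4 dates the call from week 96, and the sentence in 11.5 is explicit. A favourable reading of 11.3 leaves two sections in conflict. Women whose participation is ended by staff under section 10 have not necessarily refused contact.

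**Conclusion.** The point holds in a limited form. On the literal text of 11.5, new-onset adverse and serious adverse events are not sought after departure in women who leave the study and do not stay in follow-up. The sections that should settle the matter contradict one another and must be reconciled.

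The size is modest: at most about 13 of 128 women before week 48, plus an unstated number of later leavers. This rests on the protocol's 10% dropout and on treating every dropout as a departure without follow-up.

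A reader might infer that the between-arm comparison of event rates is materially biased. The documents do not establish that. The withdrawal rule in 11.6 is triggered by stopping TAF/FTC, which before week 48 only the immediate-switch arm takes, so some imbalance is possible. But those women may remain in follow-up, the uncovered time is about 0.4% of planned surveillance before later leavers are counted, and the completers' extra 30 days fall when both arms have been assigned TAF/FTC. The effect on arm rates is probably small. The main loss is safety information on individual women.

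**What to change.** Reconcile 11.3, 11.5 and 11.6 to one end point for adverse-event surveillance: 30 days after the last study visit, where that visit may be the early-termination visit, unless the woman withdraws consent to contact. Bring the first sentence of 11.5 into line and remove the ambiguous bracket in 11.3. In 11.6, make clear whether a woman who agrees to continued follow-up counts as withdrawn from the study for surveillance purposes. In 8.5 and the schedule of procedures, extend the existing W100 call to early leavers, timed from their last visit. While the text is open, check that the call window in 8.4 matches the 30 days stated in 11.3 and 11.5.

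The cost is one phone call per early leaver, about 13 before week 48 plus later leavers, and amendment wording. The change affects ascertainment only, not treatment. It will not recover events in women who cannot be reached or who refuse contact.

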11.6 Toxicities/ Adverse Event Management

In the event of a discontinuation of TAF/FTC for suspected renal impairment, or other clinically significant chemistry elevations, participants should not restart TDF/FTC or TAF/FTC due to the risk of a recurrent reaction; such participants should be withdrawn from study and seek/be reviewed for alternative antiretroviral therapy. If they agree, participants will continue to be followed for the duration of the study.

11.7 Management of HIV Virologic failure.

Virologic failure must be considered for any patient with plasma HIV RNA ≥ 50 c/mL at any time following randomization. For the purposes of clinical management in this study, virologic failure is defined as:

Two consecutive plasma HIV RNA ≥ 50 c/mL within four weeks of the initial suspected virologic failure.

Cases of confirmed virologic failure will trigger genotypic virologic resistance testing, including integrase resistance testing, when plasma HIV RNA >400 c/mL. The virologic failure definition is intended for guidance and Investigators should use their discretion as to the most appropriate clinical management of their patients. The choice of antiretroviral therapy will be left to the discretion of the treating physician. In some cases, e.g. if there is no evidence of acquired resistance to the current regimen, treatment may be continued with increased efforts at adherence support.

11.8 Pregnancy Management

As this study is enrolling peri and post-menopausal women the risk of pregnancy is extremely low.

11.9 Action to be taken if pregnancy occurs

Any participant who becomes pregnant during the study must be immediately withdrawn from TAF/FTC to eliminate further exposure to the embryo/foetus.

11.10 Pregnancy Reporting

If pregnancy occurs during the period of protocol-defined surveillance, while it is not considered an adverse event or serious adverse event requires monitoring and follow up. The investigator must report the pregnancy information for trial participants using a pregnancy CRF. The pregnancy should be followed up by the investigator until delivery. To ensure participant safety, each pregnancy must be reported within one week of learning of its occurrence. The pregnancy must be followed up to determine outcome (including premature termination) and status of mother and child, which must also be reported using a pregnancy outcome CRF. Pregnancy complications and elective terminations for medical reasons must be reported as an AE or SAE. Spontaneous abortions must be reported as an SAE.

Any SAE occurring in association with a pregnancy brought to the investigator's attention after the participant has completed the study and considered by the investigator as possibly related to the investigational product, must be promptly reported.

[Investigators are also encouraged to report any pregnancy that occurs during study participation to the Antiretroviral Pregnancy Registry. More information including copies of applicable CRFs and fax numbers are available at www.apregistry.com.]

12. TRIAL MANAGEMENT

12.1 Local Coordination

Each collaborating investigator will be responsible for recruiting study personnel, obtaining local REB/IRB approval, ensuring local clinic staff are informed about the study, and supervising local study activities. The study personnel at the site will be responsible for: identifying participants; obtaining informed consent; conducting study visits; ensuring participants have regular follow-up; encouraging attendance at visits; telephoning participants if visits are missed; and collecting participant data. A study manual will outline methods for CRF completion and record management. Personnel will also be trained on study procedures prior to and during the study. The informed consent forms and study questionnaires will be translated into Italian and French.

